## 1. LIST OF ABBREVIATIONS

Abbreviation	Term
AE	Adverse Event
ANCOVA	Analysis of covariance
CPP	Cancer Prevention Pharmaceuticals, Inc.
CPP-1X	Eflornithine, DFMO, Difluoromethylornithine
CRO	Contract Research Organization
CTCAE	Common Terminology Criteria for Adverse Events
DMC/DSMB	Data Monitoring Committee/Data Safety Monitoring Board
EDC	Electronic Data Capture System
EFS	Event-Free Survival
EMA	European Medicines Agency
EORTC	European Organisation for Research and Treatment of Cancer
FAP	Familial Adenomatous Polyposis
FDA	Food and Drug Administration
FFQ	Food Frequency Questionnaire
HRQoL	Health Related Quality of Life
ICH	International Conference on Harmonization
ITT	Intent-To-Treat
LGI	Lower Gastrointestinal
LGIOI	LGI Observed Improvement
LOCF	Last Observation Carried Forward
NASR	Nutrition Assessment Shared Resource (Fred Hutchinson Cancer Research Center)
NCI	National Cancer Institute
ODC	Ornithine Decarboxylase
QLQ	Quality of Life Questionnaire
SAM	S-Adenosyl Methionine
SAE	Serious Adverse Event
SAP	Statistical Analysis Plan
SAS	Statistical Analysis System
UGI	Upper Gastrointestinal
UGIOI	UGI Observed Improvement
Z-score	The value of the critical ratio (score statistic divided by its standard error) based on the stratified log-rank statistic.

## 2. INTRODUCTION

This Statistical Analysis Plan (SAP) describes the proposed statistical analysis of the Cancer Prevention Pharmaceuticals, Inc. (CPP) study CPP FAP-310 entitled: “A DOUBLE-BLIND, RANDOMIZED, PHASE III TRIAL OF THE SAFETY AND EFFICACY OF CPP-1X/SULINDAC COMPARED WITH CPP-1X, SULINDAC AS SINGLE AGENTS IN PATIENTS WITH FAMILIAL ADENOMATOUS POLYPOSIS (FAP)”.

The purpose of this document is to apply sound analytic principles through description and pre-specification of the statistical approaches and data handling conventions for key analyses and the randomization processes.

This plan will focus on analysis of the primary and secondary endpoints, intended to assess the extent to which the combination treatment (CPP-1X 750 mg daily + sulindac 150 mg daily) is more effective than each of the two single agent treatments alone (CPP-1X 750 mg daily + placebo, and sulindac 150 mg daily + placebo) in delaying the time from the date of randomization to the date of the first occurrence of any FAP-related event in FAP patients. Sample size and total FAP-related events will be discussed, along with study population definitions. In addition, we will summarize our approach regarding the analysis of safety data, pharmacokinetic data, and patient reported quality of life data. The composition, charter, and initial tasks of the Data Monitoring Committee (DMC) will be described, along with planned interim analyses.

## 3. STUDY OBJECTIVES AND ENDPOINTS

### 3.1 Overview of Study

This is a randomized, double-blind, phase III trial in patients with FAP to evaluate the safety and efficacy of the combination product 750 mg CPP-1X + 150 mg sulindac versus each of the two single-agent products: 1) 750 mg CPP-1X; and 2) 150 mg sulindac. The primary study comparisons will be made between the combination product and each single agent product, separately.

Eligible patients who have given informed consent will enter the study with the intent to participate for the full treatment period of 24 months. Based on a subject's date of randomization, patients will be offered continued preparticipation in blinded treatment for up to a total of 36, 42 or 48 months of treatment if they have completed the initial 24 months of treatment without an FAP event until one of the following occurs: 1) subject has an FAP event or comes off study for other reasons, 2) all randomized subjects have reached a minimum of 24, 36, 42 or 48 months of treatment.

A stratified randomization procedure will be used based on FAP-related time-to-first-event prognosis. The event prognosis groups are represented by 1) best (i.e., longest projected time to first FAP-related event) - rectal/pouch polyposis, 2) intermediate - duodenal polyposis, and 3) worst - pre-colectomy. If a subject has two or more of these disease sites, the most severe prognosis stratum will be assigned for randomization (e.g. worst > intermediate > best). Since an individual may have more than one disease site involved, the trial will assess time to any defined FAP-related event in the patient as a whole. In order to minimize potential treatment arm imbalance a centralized randomization process will be used to balance treatment groups within disease prognostic strata.

The stratification is predicated on the following projected event rates for the disease site specific eligibility criteria (rectal/pouch polyposis, duodenal polyposis, pre-colectomy) which are provided in the clinical study protocol (Appendix E) and summarized in Table 3.1.

**Table 3.1 Projected Event Free Rate by Disease Site**

Disease Site	Projected 2-year Event Free Rate Without Treatment
Rectum/Pouch Polyposis	Excisional intervention and/or high risk adenoma – 40 - 60%
Duodenal Polyposis	Excisional intervention, Spigelman stage progression, cancer – 50%
Pre-colectomy	Colectomy, proctocolectomy – 10%

The stratified randomization will be reflected in stratified analyses for the primary and secondary endpoints. For design purposes only, however, the following simplified assumptions were made: an overall event free proportion of 30% in the single agent treatment group and 60% in the combination treatment group after 24 months of study treatment. This is described further in Table 3.2 below. See Section 5.1 for sample size and power calculations.

**Table 3.2 Overall Event Free Proportions After Two Years of Follow-up\***

Treatment	S(t)	t (months)	Median Time to Event (months)
Combination	0.6	24	32.566
Single Agent	0.3	24	13.817

\*These proportions are assumed for design purposes only. The median times to event are based on the assumption of an exponential time-to-event function S(t) in each group.

At least 150 eligible patients will be enrolled in this study, with at least 50 per treatment group. Patients will be randomized to one of three treatment groups within the prognostic strata defined above in equal proportions (i.e., 1:1:1 randomization): 1) CPP-1X plus sulindac, 2) CPP-1X placebo plus sulindac, 3) CPP-1X plus sulindac placebo. The study is double blinded, so neither patients nor Investigator nor Sponsor will be aware of treatment assignment.

The grading of adverse events will be based on the current version of the NCI Common Terminology Criteria for Adverse Events (CTCAE Version 4.03).

Refer to the CPP FAP-310 protocol for the details of the treatment and study schedule, and description of study procedures and tests.

### 3.2 Study Objectives

The primary study analysis will be performed using the intent-to-treat (ITT) population which is defined in Section 4.1. Statistical methods for the primary analysis are described in Sections 5.1 and 5.5.3.

The primary objective of this trial is to determine whether the combination of CPP-1X + sulindac is superior to either single-agent treatment individually in delaying time from the date of randomization to the date to the first occurrence of any FAP-related event.

Thus the primary objective contains two treatment comparisons:

1. CPP-1X placebo + sulindac active vs. CPP-1X active + sulindac active,  
and
2. CPP-1X active + sulindac placebo vs. CPP-1X active + sulindac active

These two treatment comparisons will be performed sequentially, as described below.

The combination of CPP-1X active + sulindac active is specified as the reference treatment group because it is common to both comparisons. In addition, because the purpose of the combination treatment is to delay the time from randomization to FAP-related disease progression compared to single-agent treatments, formulating the hypothesis tests in this manner will allow a positive rather than a negative Z-score for the test statistic to be interpreted as supportive of this purpose.

Each comparison will be performed at the 2-sided 0.05 level of statistical significance.

As explained in Section 3.2.1 below, the decision to seek regulatory approval based upon the results of the primary objective will be taken sequentially.

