### **3.2.2 Regulatory Review of Primary Outcome Compliance**

CPP has received advice from both the FDA and the EMA concerning the test method and criteria (Sections 3.2 and 5.) to be used when analyzing the primary study outcome, including the value of alpha.

The US Food and Drug Administration (FDA) noted that the comparison of single agent CPP-1X vs. combination treatment will not provide information about the treatment effect of CPP-1X (i.e. eflornithine), and therefore this result will not be included in the product label. Therefore, the primary analysis of import to FDA is the comparison of single agent sulindac vs. combination treatment.

The European Medicines Agency (EMA) noted that for the three arm trial design the superiority of the combination treatment must be tested against both mono-components. The combination treatment must be shown to be superior to both mono-components, or else the results will be considered inconclusive. As a consequence, consistent with EMA/SAWP commentary, alpha does not need to be adjusted for multiplicity and two separate 5% two-sided tests will suffice.

To harmonize the advice provided by these two Agencies, CPP will sequentially perform the two primary comparisons as part of the primary analysis, each at the 2-sided  $p = 0.05$  level. All information concerning these comparisons will be clearly provided to both Agencies. The single treatment comparison requested by FDA will be available, as will the two comparisons requested by EMA, both at the requested level of alpha. This approach fulfills the differing requirements for the primary comparison as asked for by each Agency.

We note that this approach is both a fixed-sequence and gatekeeping approach. It is fixed-sequence in that the comparison of combination with single-agent Sulindac takes place before the comparison of combination with single-agent Eflornithine and the first serves as a gatekeeper for the second (i.e., no declaration of significance in the second comparison will be made if the first comparison is not significant at the 0.05 level). Therefore, the type I error in the sequential testing is well controlled. In addition, because *both* tests must be significant for EMA approval, the type I error of the second test in the sequence is less than 0.05.

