These binary UGIOI and LGIOI secondary efficacy endpoints will be compared in a manner analogous to the primary analysis, using the same two primary treatment comparisons (1: CPP-1X placebo + sulindac active vs. CPP-1X active + sulindac active; and 2: CPP-1X active + sulindac placebo vs. CPP-1X active + sulindac active), and conditioning on the three disease site strata (Rectum/Pouch Polyposis, Duodenal Polyposis, Pre-colectomy). The null hypothesis of no association between treatment group and Improvement endpoints will be tested using the exact Mantel-Haenszel procedure for combining the evidence contained in the fourfold tables (Treatment=Single agent vs. Combination cross-classified by Improvement=YES vs. NO) across the three strata. For each of the two treatment comparisons, exact Mantel-Haenszel p-values will be calculated for both the UGI and LGI assessments (using the point-probability method based

on the convolution of three independent central hypergeometric distributions; see [1]).

The overall type I error for the secondary efficacy analysis will be controlled using the Hochberg step-up method for multiple comparisons[2]. This analysis will be performed in the ITT population. The primary analysis will serve as a gatekeeper to control the overall type I error rate at 0.05 for both primary and secondary analyses. That is, significance for the secondary efficacy analysis will be declared only if the primary p-value is 0.05 or less, when the p-values are tested sequentially per the Hochberg method[2].

Further analyses of the secondary endpoints may be conducted to evaluate and provide additional evidence to support its validity and confirm its clinical relevance.

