##### **5.4.2 Prespecified Interim Efficacy and Futility Analysis**

A pre-specified interim efficacy and futility analysis will be conducted as described below. The assessment will be performed after a total of 45 primary endpoints have occurred, which represents 50% of expected maximum trial information, or as soon thereafter as possible. After reviewing the analysis results in a closed session, the DMC will provide recommendations regarding possible termination of the study for either futility, efficacy, or safety reasons, to the Sponsor Steering Committee.

The analysis will be performed for each of the two treatment comparisons contained in the

primary objective:

1. CPP-1X placebo + sulindac active vs. CPP-1X active + sulindac active,  
and
2. CPP-1X active + sulindac placebo vs. CPP-1X active + sulindac active.

As stated above in Section 3.2, the combination of CPP-1X active + sulindac active is specified as the reference treatment group because it is common to both comparisons and formulating the hypothesis tests in this manner will allow a positive rather than a negative Z-score for the test statistic to be interpreted as supportive of this purpose.

The efficacy analysis will use a modified Haybittle-Peto stopping rule based on the stratified log-rank Z-score. If that Z-score equals or exceeds 3.2905 in absolute value, for either two-arm comparison, the difference between treatment arms would be declared statistically significant at the two-tailed 0.001 level of significance. In that case it may be reasonable for the DMC to initiate a conversation about stopping the trial on ethical grounds. Assuming this is not the case and the trial continues to its planned end, the Z-score criterion for declaring significance at the 5% level at the end of the trial will be increased in magnitude to plus or minus 1.962 in order to preserve the overall type I error rate for the trial at 0.05.

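### SAP 3.2.3 opens secondary testing at a primary p of 0.05 or less, but the final primary criterion in SAP 5.4.2 is |Z| ≥ 1.962 (two-sided p ≤ 0.0498)

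*SAP*

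**What the plan says.** **Level of the primary tests.** SAP 3.2 states "Each comparison will be performed at the 2-sided 0.05 level of statistical significance", and Protocol 12.1 says the same. For methods, SAP 3.2 directs the reader as follows: "Statistical methods for the primary analysis are described in Sections 5.1 and 5.5.3". Neither of those sections gives a final critical value. SAP 3.2.2 adds "CPP will sequentially perform the two primary comparisons as part of the primary analysis, each at the 2-sided" p = 0.05 level, and makes the sulindac comparison a condition for the CPP-1X comparison: "no declaration of significance in the second comparison will be made if the first comparison is not significant at the 0.05 level".

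**Final critical value.** SAP 5.4.2 places an efficacy look at 45 events, taken as half of the information. The boundary reads "If that Z-score equals or exceeds 3.2905 in absolute value, for either two-arm comparison". If the trial continues, the final criterion "will be increased in magnitude to plus or minus 1.962 in order to preserve the overall type I error rate for the trial at 0.05". Table 5.1 lists 1.962 as the terminal efficacy criterion. SAP 7.4 uses it as the two-tailed critical value for alpha 0.05 after adjustment for the interim look. Protocol 12.8 repeats the 5.4.2 rule.

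**Entry to the secondary family.** SAP 3.2.3 makes the primary analysis the gatekeeper for UGIOI and LGIOI, so that error is held at 0.05 over primary and secondary analyses together. The condition is: "significance for the secondary efficacy analysis will be declared only if the primary p-value is 0.05 or less".

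**The concern.** A gatekeeping procedure protects the later family only if the condition for entering it is the same event as success at the earlier step. In SAP 3.2.3 it is not. The entry condition is a p-value of 0.05, which corresponds to |Z| ≥ 1.95996, while primary success at the final analysis needs |Z| ≥ 1.962. A result between the two fails the primary test and still lets UGIOI and LGIOI be declared significant.

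The sections on the primary tests are less clear than they should be. SAP 3.2 and Protocol 12.1 name the 0.05 level without pointing to the adjusted criterion, and the phrasing in SAP 3.2.2 as a p of 0.05 invites a nominal reading. At stake is whether a borderline final result leaves room for argument, after unblinding, about what was pre-specified.

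**Working it through.** **Inputs.** Interim boundary 3.2905, final criterion 1.962 and futility value −0.50 (SAP 5.4.2); information fraction 0.5 (SAP 5.4.2); log hazard ratio 0.85736 and information equal to events/4 (SAP 7.4).

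**1. Nominal p of the final criterion.** 2Φ(−1.962) = 0.04976. The critical value for a nominal two-sided 0.05 is 1.95996.

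**2. Reproducing Table 5.1.** I used the formula in its footnote, with the futility bound applied:

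- Upper = Φ(−3.2905) + ∫ from −0.5 to 3.2905 of Φ(z − C√2)φ(z)dz
- Lower is the same with Φ(−z − C√2)

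| C | Upper | Lower | Total |
|---|---|---|---|
| 1.962 | 0.024952 | 0.001984 | 0.026936 |
| 1.9602 (printed in the footnote) | 0.025056 | 0.001996 | 0.027052 |
| Table 5.1 as printed | 0.024952 | 0.001928 | 0.026936 |

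The printed upper and total figures match 1.962, so that is the value the design used. The printed lower figure does not add up: 0.024952 + 0.001928 = 0.026880.

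**3. Overall two-sided error, futility non-binding.** Error = 2[Φ(−3.2905) + ∫ from −3.2905 to 3.2905 of Φ(z − C√2)φ(z)dz].

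- C = 1.95996: 0.05022
- C = 1.962: 0.04999
- The exact value for 0.05 is C = 1.9619

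**4. The same with the futility bound applied.**

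- C = 1.95996: efficacy tail 0.02507, two-sided total 0.02707
- C = 1.962: efficacy tail 0.02495, two-sided total 0.02694

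**5. What the SAP 3.2.3 clause adds by itself.** Suppose the primary is judged at 1.962 and secondary entry at p ≤ 0.05. With futility non-binding, an extra false claim needs a final Z in the band and then a secondary rejection. Under the null for both, the added error per comparison is at most 0.05022 − 0.04999 = 0.00023.

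**6. Chance that the final Z lands in the band (1.95996 to 1.962 in absolute value).** These figures ignore early stopping.

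- Null: 0.05000 − 0.04976 = 0.00024
- Design hazard ratio, mean of Z = 0.85736√(d/4):
  - d = 43: mean 2.811, probability 0.00057
  - d = 49: mean 3.001, probability 0.00047
  - d = 55: mean 3.179, probability 0.00039

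**7. Sensitivity to the timing of the look.** The documents plan for 0.5. As an assumed range, a fraction of 0.4 needs C = 1.9631, and 1.962 then gives 0.0501. A fraction of 0.6 needs C = 1.9609, and 1.962 then gives 0.0499.

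**The case against.** A reader might infer that the plan sets two rival thresholds for the primary tests themselves, and that its claim to hold type I error at 0.05 is false on its own reasoning. The documents do not support that.

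- SAP 5.4.2 presents 1.962 as the criterion for significance at the 5% level, and SAP 7.4 calls it the critical value at alpha 0.05. In a group-sequential plan, alpha and the final critical value are different quantities. The 0.05 level in SAP 3.2, SAP 3.2.2 and Protocol 12.1 can therefore be read as the overall alpha. No section prints 1.95996.
- SAP 3.2.2 refers to Sections 3.2 and 5 for the test method and criteria, and Section 5 includes 5.4.2. The adjusted criterion can be found from there, even though SAP 3.2 points elsewhere.
- The SAP's own error calculation in Table 5.1 applies the futility bound. On that basis the two-sided total is about 0.027 under either cut-off, and only the efficacy tail passes 0.025, by 0.00007. An excess over 0.05 appears only with futility non-binding. The wording of 5.4.2 supports that reading, since the rule starts an investigation and does not force a stop, but Table 5.1 does not calculate it.
- Ordinary drift in the timing of the look moves the error by a similar amount (step 7).

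All of this stands, and it limits the point to wording in SAP 3.2, SAP 3.2.2 and Protocol 12.1. It does not rescue SAP 3.2.3, where a p-value of 0.05 or less cannot be read as an overall alpha. No other section corrects that clause.

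**Conclusion.** The point holds for SAP 3.2.3: its entry condition for secondary testing is looser than the final primary criterion in SAP 5.4.2, Table 5.1 and SAP 7.4. For SAP 3.2, SAP 3.2.2 and Protocol 12.1 it is a matter of clarity only, namely a missing pointer to the adjusted criterion.

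The severity is minor. The two rules part only for a final p between 0.04976 and 0.05. The error figures assume one look at half the information; the 0.0502 also assumes non-binding futility. The reason to act is that a confirmatory plan should leave no choice of threshold once the data are unblinded. The size of the inflation would not justify it. Nothing here shows a defect in the two-sided form of the criterion, and that form should stay.

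**What to change.** - **SAP 3.2.3:** replace the condition of a primary p of 0.05 or less with: *the primary comparison meets the final criterion of Section 5.4.2 (|Z| ≥ 1.962, two-sided nominal p ≤ 0.0498)*.
- **SAP 3.2, SAP 3.2.2 and Protocol 12.1:** keep the overall two-sided alpha of 0.05. Add that significance at the final analysis, and the condition for proceeding to the CPP-1X comparison, mean |Z| ≥ 1.962 as set in SAP 5.4.2 (Protocol 12.8).
- **Table 5.1, while the text is open:** bring the footnote value 1.9602 into line with 1.962, and correct the lower-boundary figure to 0.001984.

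The cost is wording in the SAP and protocol. Sample size, data collection and conduct do not change, and the criterion is the one SAP 5.4.2 already adopts.

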### **3.2.1 Primary Analysis**

The primary analysis will be a time-to-event analysis using the stratified log-rank test. Graphical analyses (log-minus-log plots) will be used to check the assumption of constant hazard ratios with the COX model. See Section 7.3 below for further details of the calculation of the stratified log-rank statistic. The strata are the patient's sites of disease involvement at baseline, which is determined prior to randomization, and are: Rectal/pouch polyposis, Duodenal polyposis, and Pre-colectomy.

For the primary analysis, two stratified log-rank tests will be performed with treatment coded as a binary value (i.e., 0 or 1). Time to event curves will be displayed using the method of Kaplan and Meier[8]. Additional analyses involving the overall 3-treatment group comparison and use of additional study populations (see Section 4.) for the two pairwise treatment comparisons, will be performed as supplemental analyses. Refer to section 5.5.3 for further details.

### **3.2.2 Regulatory Review of Primary Outcome Compliance**

CPP has received advice from both the FDA and the EMA concerning the test method and criteria (Sections 3.2 and 5.) to be used when analyzing the primary study outcome, including the value of alpha.

The US Food and Drug Administration (FDA) noted that the comparison of single agent CPP-1X vs. combination treatment will not provide information about the treatment effect of CPP-1X (i.e. eflornithine), and therefore this result will not be included in the product label. Therefore, the primary analysis of import to FDA is the comparison of single agent sulindac vs. combination treatment.

The European Medicines Agency (EMA) noted that for the three arm trial design the superiority of the combination treatment must be tested against both mono-components. The combination treatment must be shown to be superior to both mono-components, or else the results will be considered inconclusive. As a consequence, consistent with EMA/SAWP commentary, alpha does not need to be adjusted for multiplicity and two separate 5% two-sided tests will suffice.

To harmonize the advice provided by these two Agencies, CPP will sequentially perform the two primary comparisons as part of the primary analysis, each at the 2-sided  $p = 0.05$  level. All information concerning these comparisons will be clearly provided to both Agencies. The single treatment comparison requested by FDA will be available, as will the two comparisons requested by EMA, both at the requested level of alpha. This approach fulfills the differing requirements for the primary comparison as asked for by each Agency.

We note that this approach is both a fixed-sequence and gatekeeping approach. It is fixed-sequence in that the comparison of combination with single-agent Sulindac takes place before the comparison of combination with single-agent Eflornithine and the first serves as a gatekeeper for the second (i.e., no declaration of significance in the second comparison will be made if the first comparison is not significant at the 0.05 level). Therefore, the type I error in the sequential testing is well controlled. In addition, because *both* tests must be significant for EMA approval, the type I error of the second test in the sequence is less than 0.05.

